7.0 Demographics, Baseline Characteristics, Medical History, and Prior/Concomitant Medications

Demographics, baseline or disease characteristics, medical history, and prior and concomitant medications will be summarized for the ITT1A and ITT1B populations overall and by treatment group. Categorical variables will be summarized with the number and percentage of subjects; percentages will be calculated based on the number of non-missing observations. Continuous variables will be summarized with descriptive statistics (number of non-missing observations, mean and standard deviation, median, minimum and maximum).

7.1 Demographics and Baseline Characteristics

The following demographic, as measured at baseline of the study, will be summarized.

Continuous variables:

- Age (years)
- Body weight (kg)
- Body weight – Female (kg)
- Body weight – Male (kg)
- Height (cm)
- Height – Female (cm)
- Height – Male (cm)
- Body Mass Index (kg/m²)

Categorical variables:

- Sex (male, female)
- Age (< 18, 18 - < 40, 40 - < 65, ≥ 65)
- Race (American Indian/Alaska Native, Asian, Black or African American, Native Hawaiian or Other Pacific Islander, White, Multiple)
- Race (White, Non-White)
- Ethnicity (Hispanic or Latino, Not Hispanic or Latino)
- Tobacco use (Never, current, former, unknown)
- Alcohol use (Never, current, former, unknown)
- Body Mass Index (kg/m²):
 - Underweight [< 18.5 kg/m²]
 - Normal [≥ 18.5 and < 25 kg/m²]
 - Overweight [≥ 25 and < 30 kg/m²]
 - Obese [≥ 30 kg/m²]

The following baseline characteristics, as measured at baseline of the study, will be summarized.

Continuous variables:

- Blood Pressure (systolic/diastolic) (mmHg)
- Pulse (bpm)
- Respiratory Rate (RPM)
- Temperature (°C)
- IBDQ total score and its components
- Full Mayo score and its components (stool frequency, rectal bleeding, PGA, and endoscopy subscores)
- Partial Mayo score
- Adapted Mayo score
- hs-CRP (mg/L)
- Fecal Calprotectin (mg/kg)
- Albumin (g/L)
- Short Form 36 Health Survey (SF-36) and its components
- European Quality of Life 5 Dimensions 5 Levels (EQ-5D-5L)
- Functional Assessment of Chronic Illness Therapy-Fatigue (FACIT-F)
- WPAI and its components
- Ulcerative Colitis Symptoms Questionnaire (UC-SQ)
- Disease duration

Categorical variables:

- Baseline corticosteroid use (yes, no)
- Baseline immunosuppressant use (yes, no)
- Baseline aminosalicylates use (yes, no)
- Baseline anti TNF use (yes, no)
- Baseline biologics use (yes, no)
- Baseline hs-CRP (≤ 5 mg/L, > 5 mg/L)
- Disease duration (≤ 3 years, > 3 years)

- Disease extent (left-sided, extensive/pancolitis, limited to rectum)
- Region (US, ex-US)

In addition, clinical tests including TB test and electrocardiogram assessment at screening will be summarized.

7.2 Medical History

Medical history data will be coded using the Medical Dictionary for Regulatory Activities (MedDRA). The actual version of the MedDRA coding dictionary will be noted in the statistical tables and clinical study report. The number and percentage of subjects in each medical history category (by MedDRA system organ class and preferred term) will be summarized overall and by treatment group for the Induction Period 1 ITT1A, ITT1B and the Induction Period 2 ITT1_P2 Populations. The system organ class (SOC) will be presented in alphabetical order, and the preferred terms will be presented in alphabetical order within each SOC. Subjects reporting more than one condition/diagnosis will be counted only once in each row (SOC or preferred term).

7.3 Prior and Concomitant Medications

Prior and concomitant medications including UC specific medications (corticosteroids, aminosalicylates, immunosuppressant agents, and UC-related antibiotics) that the subject has received within 90 days of baseline will be summarized by generic name. A prior medication is defined as any medication taken prior to the date of the first dose of study drug. This includes medications with a start date before the first study drug administration date, regardless of the end date of these medications. Medications taken on the day of the first dose of study drug are not counted as prior medications.

A concomitant medication is defined as any medication that started prior to the date of the first dose of study drug and continued to be taken after the first dose of study drug or any medication that started on or after the date of the first dose of study drug, but not after the date of the last dose of study drug plus 140 days. The number and percentage of subjects

taking medications will be summarized by generic drug name based on the World Health Organization (WHO) Drug Dictionary for both prior and concomitant medications.

8.0 Efficacy Analyses

8.1 General Considerations

The primary and secondary efficacy endpoints will be analyzed based on ITT1A in Induction Period 1 of Sub-Study 1 as the primary analysis.

The primary and ranked secondary efficacy endpoints will be analyzed based on ITT1B in Induction Period 1 of Sub-study 1 as the exploratory analysis.

All analyses for the efficacy endpoints in Induction Period 2 will also be performed based on ITT1_P2 for Sub-Study 1 for exploratory purpose.

For all efficacy endpoints, the descriptive statistics will be provided by treatment group for each induction period in each sub-study. The statistics include number of observations, mean, standard deviation, minimum, median, and maximum for continuous variables; and number and percentage of subjects for categorical variables.

8.2 Handling of Missing Data

UC-related corticosteroids Censoring

For both Periods 1 and 2, the following subjects will be censored for efficacy assessments from that point through the end of the study.

- subjects not on UC-related corticosteroids (systemic or locally acting corticosteroids for UC) at Baseline who then initiated during the study or
- subjects on UC-related corticosteroids who have dosages increased to greater than the dose taken at Baseline.

I.e., these subjects will be considered as 'Not Achieved' for binary endpoints (Y/N) and any non-missing continuous assessments after censoring will not be used in the analysis

For composite endpoint, censoring will be applied on each component before calculating the composite endpoint. If any component is censored, the composite endpoint will be considered as censored. These subjects will continue to be evaluated in the safety population. In addition, hospitalizations and UC-related surgeries will not be censored.

Handling of Missing Data

Missing data will be imputed using the following methods for the efficacy analyses.

- Observed Cases (OC): The OC analysis will not impute values for missing evaluations, and thus a subject who does not have an evaluation on a scheduled visit will be excluded from the OC analysis for that visit. All the other imputations will be performed after OC.
- Non-Responder Imputation (NRI): The NRI approach is used for binary efficacy variables. These variables can take values of 'Achieved' or 'Not Achieved' or may be. According to the NRI approach, all missing values will be considered as 'Not Achieved.'
- Last Observation Carried Forward (LOCF): The LOCF analyses will use the completed evaluation from the previous visit for efficacy measures assessed to impute missing data at later visits. Baseline and Pre-Baseline value will not be used for the imputation. If there are no non-missing values after the Baseline, then the LOCF value also will be missing.
- Mixed-Effect Model Repeat Measurement (MMRM): The repeated measures analysis will be conducted using a mixed model including OC at all visits. The mixed model includes the categorical fixed effects of treatment, visit and treatment-by-visit interaction, main stratification factors at randomization, and the continuous fixed covariates of baseline measurement. An unstructured variance covariance matrix will be used. Parameter estimation is based on the assumption of data being missing at random and using the method of restrictive maximum likelihood (REML).
- Hybrid Multiple Imputation Method. Primary endpoint of clinical remission will be analyzed using hybrid multiple imputation (MI) method. Subjects who discontinue study prior to Week 12 due to lack of efficacy or AEs will be considered as "not achieved" for clinical remission. Subjects who discontinue

for other reasons will be categorized according to multiple imputations. MI approach will be used as a sensitivity analysis for the primary endpoint. For the primary endpoint, 20 'complete' datasets will be generated using SAS PROC MI. The seed will be 12345. The imputed post-baseline measurements will be rounded to the same precision as the observed data before the determination of responder status. Using the Cochran-Mantel-Haenszel (CMH) model adjusted by main stratification factors, the imputed endpoints will be analyzed using each of the 20 datasets. SAS PROC MIANALYZE will be used to generate the final inferences of the risk difference between treatment groups.

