8.1.6.2 Secondary Efficacy Variables

Sub-Study 1 – Induction Period 1:

For Induction Period 1 in Sub-Study 1, the secondary efficacy variables listed in Section 5.3.3.2 were analyzed by treatment group for ITT1A as the primary analysis at the nominal α level of 0.05 (one-sided).

Categorical secondary efficacy endpoints were analyzed using CMH controlling for stratification variables. NRI imputation were used for primary inference purpose except for occurrence of hospitalization and UC-related surgeries of which as observed data were used. Continuous secondary efficacy endpoints were analyzed using a Mixed-Effect Model Repeated Measures (MMRM) method as the primary analysis.

Additional analysis based on ITT1 with additional subjects enrolled into risankizumab 1800 mg IV will be conducted separately as exploratory purpose.

No multiplicity adjustment will be performed.

Sub-Study 2 – Induction Period 1:

The secondary efficacy endpoints will be compared between the subjects in risankizumab dose group and placebo group based on ITT2.

Categorical secondary efficacy endpoints will be analyzed using the same CMH test as that for primary endpoint as specified in Section 8.1.6.1.1. NRI-MI, as defined in Section 8.1.2, will be the primary approach for missing data handling in the analyses of

categorical secondary efficacy endpoints except for UC-related hospitalization, of which AO data will be used.

Continuous secondary efficacy endpoints will be analyzed using RTB-MI as defined in Section 8.1.2 with MMRM (for endpoints with more than one post-baseline visits) or with ANCOVA (for endpoints with one post-baseline visit) models.

For all endpoints specified in Section 5.3.3.2, descriptive summary will be provided for ITT1_P2 and ITT2_P2 for exploratory purposes.

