8.0 Handling of Potential Intercurrent Events

The primary efficacy endpoint of clinical remission per Adapted Mayo score at Week 12 (defined in Section 3.1) and the secondary efficacy endpoints (defined in Section 3.2) will be analyzed based on the ITT2 population. The following methods will be used to address potential intercurrent events (IEs):

- IE1. Premature discontinue from the study drug:
 - Data collected will be used regardless of premature discontinuation of study drug.
- IE2. Initiation or dose escalation of UC-related corticosteroid event defined as:
 - Subjects not on UC-related corticosteroids (systemic or locally acting corticosteroids for UC) at baseline who then initiated UC-related corticosteroids during the Induction study.
 - Subjects on UC-related systemic corticosteroids at baseline who have dosages increased to greater than the prednisone equivalent dose of corticosteroid taken at baseline, or initiation of any rectal corticosteroids during the Induction study regardless of rectal corticosteroid dose.
 - Subjects on UC-related rectal corticosteroids at baseline who have dosages increased to greater than the dose taken at baseline, or initiation of any new type of rectal or any systemic corticosteroids during the Induction study.

The time point of the UC-related corticosteroids intercurrent event is defined as the date when one of the scenarios above occurs for a subject. As such, subjects will be considered as "non-responder" for binary endpoints on or after the date of the UC-related corticosteroids intercurrent event through the end of the Induction study in the primary analysis (except for the occurrence of UC-related hospitalization and UC-related surgeries). For continuous endpoints, all measurements on or after the date of the UC-related corticosteroids intercurrent event through the end of the Induction study will not be used in the primary analysis.

- IE3. UC-Related Surgery (ileostomy, colectomy, or proctocolectomy):
The time point of the UC-related surgery (ileostomy, colectomy, or proctocolectomy) intercurrent event is defined as the date of the first UC-related surgery. All measurements on or after the date of the UC-related surgery (ileostomy, colectomy, or proctocolectomy) will be handled similarly as UC-related corticosteroid intercurrent events.

For the additional Period 1 efficacy endpoints and Induction Period 2 efficacy endpoints similar methods to address potential intercurrent events will be applied.

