3.2 Secondary Endpoint(s)

The secondary endpoints for Sub-Study 1 are:

Ranked Secondary Endpoints:

1. The achievement of endoscopic improvement at Week 12
2. The achievement of clinical remission per Full Mayo score at Week 12 in subjects with a Full Mayo score of 6 to 12 at Baseline
3. The achievement of clinical response per Adapted Mayo score at Week 12
4. The achievement of clinical response per Partial Adapted Mayo score at Week 4
5. The achievement of endoscopic remission at Week 12
6. Occurrence of hospitalizations through Week 12
7. The achievement of mucosal healing at Week 12
8. Change from Baseline in UC-Symptom Questionnaire (UC-SQ) at Week 12
9. Change from Baseline in Inflammatory Bowel Disease Questionnaire (IBDQ) at Week 12
10. Change from Baseline in Short Form-36 at Week 12
11. Change from Baseline in Functional Assessment of Chronic Illness Therapy-Fatigue (FACIT-F) at Week 12
12. UC-related surgeries through Week 12

Non-Ranked Secondary Efficacy Endpoints:

- The achievement of SFS = 0, RBS = 0, and endoscopic subscore = 0 at Week 12
- The achievement of SFS \leq 1 over time
- The achievement of RBS = 0 over time
- Change from Baseline in Partial Adapted Mayo score over time
- Change from Baseline in Full Mayo score at Week 12
- Change from Baseline in SFS over time
- Change from Baseline in RBS over time
- Change from Baseline in hs-CRP over time

- Change from Baseline in FCP over time
- Change from Baseline in Ulcerative Colitis Endoscopic Index of Severity (UCEIS) at Week 12
- The achievement of histologic remission at Week 12
- Change from Baseline in European Quality of Life 5 Dimensions (EQ-5D-5L) over time
- Change in Work Productivity and Impairment Questionnaire – UC (WPAI-UC) over time
- Time to clinical response per partial adapted Mayo score
- Change from baseline in Patient Global Impression of Severity (PGIS) over time
- Patient Global Impression of Change (PGIC) over time
- The achievement of clinical remission per Adapted Mayo over time
- The achievement of endoscopic improvement over time
- The achievement of endoscopic remission over time
- The achievement of no bowel urgency at Week 12
- The achievement of no abdominal pain at Week 12
- Achieving response in IBDQ bowel symptom domain (increase of IBDQ bowel symptom domain score ≥ 6 from baseline) at Week 12
- Change from Baseline in subject-reported stool frequency (absolute values)

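### In Sub-Study 1 only steroid events count as treatment failure, so non-endoscopic scores recorded after UC-related surgery are analysed as drug outcome

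*SAP*

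**What the plan says.** Section 8.2 of the Sub-Study 1 SAP (November 2020) names two kinds of subject whose efficacy data are censored, in both induction periods. The first concerns new steroid use: "subjects not on UC-related corticosteroids (systemic or locally acting corticosteroids for UC) at Baseline who then initiated during the study or". The second concerns a dose increase: "subjects on UC-related corticosteroids who have dosages increased to greater than the dose taken at Baseline". The list ends there. After either event, binary endpoints become 'Not Achieved', and "any non-missing continuous assessments after censoring will not be used in the analysis". The paragraph closes with "In addition, hospitalizations and UC-related surgeries will not be censored".

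The same section defines NRI as setting missing binary values to 'Not Achieved'. For continuous scores it says "The repeated measures analysis will be conducted using a mixed model including OC at all visits".

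Surgery is foreseen: "UC-related surgeries through Week 12" is ranked endpoint 12 in section 3.2.

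The Sub-Study 2 SAP (version 2.0, February 2023) lists surgery as intercurrent event IE3 in section 8.0: "All measurements on or after the date of the UC-related surgery (ileostomy, colectomy, or proctocolectomy) will be handled similarly as UC-related corticosteroid intercurrent events". Its version history shows that this was added after agency feedback.

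**The concern.** A colectomy or diverting ileostomy for UC normally means that medical treatment has not controlled the disease. It can also change symptoms without any drug effect: under Protocol Appendix E the rectal bleeding subscore is 0 on a day with no visible blood in the stool. A subject operated on before Week 12 who still fills in the diary or a questionnaire could therefore count as a responder, or add an ordinary change score, while a subject given a steroid course is failed or dropped.

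The protocol already treats the surgical state as unsuitable for evaluation at entry. Exclusions 19 and 20 bar previous colectomy, ostomy and ileoanal pouch, and the rationale given in section 5.2.2 is that UC complications may compromise the evaluation of efficacy and safety. The same state arising after randomization has no rule in Sub-Study 1.

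At stake is the meaning of the symptom and quality-of-life comparisons. Endpoints with the same names also follow different rules in the two sub-studies.

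**Working it through.** **1. The plan's own figure.** Sub-Study 1 SAP section 2.4 gives 60 subjects per group, remission of 7% on placebo and at most 25% on risankizumab, one-sided 5%, and average MCP-Mod power of about 87%. I recomputed this as a maximum-contrast test at 0, 600, 1200 and 1800 mg with the five candidate shapes, optimal contrasts and pooled variance on the probability scale. Average power is 87.8% with the linear shape (section 2.4) and 87.2% to 87.3% with the log-linear shape (section 8.3.3; the log offset is my assumption). The figure reproduces. Other variance choices give 84% to 86% (logit scale) and 92% to 94% (unpooled). The calculation concerns clinical remission, which needs an endoscopic subscore, so the surgery rule does not enter it.

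**2. What happens to a subject after surgery under 8.2**

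| Endpoint type | Value missing | Value recorded |
|---|---|---|
| Binary, needs endoscopy (remission, endoscopic improvement, Adapted Mayo response and similar) | 'Not Achieved' by NRI | Scored as observed, but only if an endoscopy is still done |
| Binary, no endoscopy (Partial Adapted Mayo response, SFS ≤ 1, RBS = 0, no bowel urgency, no abdominal pain) | 'Not Achieved' by NRI | Scored as observed |
| Continuous (UC-SQ, IBDQ, SF-36, FACIT-F) | Not imputed; mixed model assumes missing at random | Enters the mixed model |

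The gap is the right-hand column of the last two rows. The sensitivity analyses do not close it. Observed-case analysis uses the recorded values. LOCF can carry them forward. The hybrid imputation that fails discontinuations for lack of efficacy or adverse events applies to the primary endpoint only.

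**3. Can such values exist?** Protocol section 5.4.1 does not name UC surgery among the withdrawal events. It asks for the premature-discontinuation visit within 2 weeks of the last dose. Appendix C schedules diary review, UC-SQ, IBDQ, SF-36 and FACIT-F at Week 12/PD.

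**4. Size, binary endpoint.** One operated subject counted as a responder in an arm of 60 adds 1/60 = 1.67 percentage points to that arm. With k such subjects on risankizumab and m on placebo, the difference moves by (k − m)/60. One on risankizumab gives +1.7 points, one on placebo gives −1.7, and one on each gives 0. For an assumed one to three in a single arm the range is 1.7 to 5.0 points in either direction.

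**5. Size, continuous endpoint.** Let D be the operated subject's change minus the mean change of the other 59. Keeping rather than dropping that value shifts the raw arm mean by D/60. For assumed IBDQ values of D of 16, 32 and 64 points, the shift is 16/60 = 0.27, 32/60 = 0.53 and 64/60 = 1.07 points per subject. The value 16 is the IBDQ response threshold in Protocol section 5.3.3.2. D may be negative.

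**The case against.** Several stronger readings are tempting, and the documents do not support them.

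- **A reader might take the closing sentence of 8.2 as an instruction to ignore surgery.** It ends a paragraph on steroid censoring and most naturally means that hospitalization and surgery stay counted after a steroid event. Protocol section 8.1.6.2 agrees: "NRI imputation were used for primary inference purpose except for occurrence of hospitalization and UC-related surgeries of which as observed data were used". The gap rests on the steroid-only list, not on this sentence.
- **A reader might infer that dose selection was distorted.** MCP-Mod was run on clinical remission, and Protocol section 5.6.4 names clinical remission, clinical response and endoscopic remission for the exposure-response work. If clinical response there means the Adapted Mayo definition, all three need an endoscopic subscore. Section 5.6.4 also mentions other clinical endpoints but names no quality-of-life score.
- **A reader might assume that the bias favours placebo because placebo should have more surgery.** No document says which arm has more, or that IBDQ, SF-36 or FACIT-F improve within weeks of an operation. They could worsen.
- **A reader might quote 5 percentage points as the expected size.** That needs three operated subjects in one arm, all scored as responders, and none in the comparator. Exclusion 19 also removes subjects whose disease might require surgery during the study.
- **A reader might call the two SAPs contradictory.** The Sub-Study 2 rule came later, and Protocol section 5.6.1 says that efficacy data from the two parts are not combined for inference.

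Other points against also have force. Opportunity is limited: the ranked Partial Adapted Mayo endpoint is at Week 4, and in Period 1 IBDQ, SF-36 and FACIT-F have one post-baseline collection. Sub-Study 1 is dose-finding without multiplicity control, and ranked endpoint 12 would show an imbalance in surgeries. Using data regardless of surgery is also a possible estimand.

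These points limit the consequence. They do not close the gap: nothing in 8.2 says that post-surgery data were meant to count, and the sponsor later adopted the opposite rule for the same event.

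**Conclusion.** The concern holds in a limited form. Section 8.2 has no rule for UC-related surgery, so symptom and questionnaire values recorded after it are treated as ordinary drug outcome. The primary and other endoscopic endpoints are largely protected because a missing endoscopy becomes 'Not Achieved', and the stated power is unchanged.

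The effect is 1.7 percentage points per misclassified subject on a non-endoscopic binary endpoint, and D/60 on a continuous score. The total depends on how many surgeries occurred, in which arms, and whether scores were collected afterwards. The documents give none of these, so both total and direction are unknown. If no subject had surgery, there is no effect. This is a small improvement worth making, not a threat to the conclusions of Sub-Study 1.

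**What to change.** Add UC-related surgery (ileostomy, colectomy or proctocolectomy) to the list in Sub-Study 1 SAP section 8.2. From the date of the first such surgery, the subject is 'Not Achieved' for all binary endpoints except hospitalization and surgery, and later continuous values are not used. This is what 8.2 already does for steroid events, and it matches the classification of surgery as IE3 in Sub-Study 2.

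The Sub-Study 2 return-to-baseline imputation should not be imported. It is absent from the Sub-Study 1 SAP and would treat surgery differently from steroid events there.

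Because the Period 1 dose-selection analysis is already done, apply the rule there as a supplementary analysis, labelled as such, and report the number of UC-related surgeries by arm. If there were none, that line closes the matter.

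The cost is a short addition to the SAP, one repeated analysis and a few observed values left unused. It assumes that surgery dates are in the database; the documents make surgery an endpoint but do not state this for Sub-Study 1.
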